## 14.5 Sample Size and Randomization

We used the UCSF Clinical & Translational Science Institute web-based sample size calculator (<http://www.sample-size.net/sample-size-means/>) to determine study size. Based on previous Nuss procedures over the past 2 years at our institution, we determined the mean length of hospitalization was 7 days, with a standard deviation of 1.3 days. From anecdotal data from our prior experience, as well as from speaking with other surgeons utilizing cryoablation, we expect patients in the cryoanalgesia group to have approximately 2 days shorter hospital stay. With type I error rate of 0.05 and type II error rate of 0.1 (yielding 90% power), our study would need 18 patients total. Allowing for some dropout, we will plan to enroll 20 patients to the study.

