STATISTICS Primary Analysis Plan	Patient baseline characteristics will be analyzed with descriptive statistics (ie. mean age, % male, mean pectus severity index, etc.). Our primary outcome will be post-operative length of stay, which will be analyzed using a two-tailed unpaired t test, with results considered statistically significant for $p < 0.05$ . Secondary outcomes include post-operative pain scores, pain medication usage, and side effects. Pain scores will be analyzed with Mann-Whitney rank sum tests (to compare between groups at each time point) and Wilcoxon signed-rank test (to compare scores within groups over time), with results considered statistically significant for $p < 0.05$ . Pain medication usage between the two groups will be analyzed with two-tailed unpaired t test, again with results considered statistically significant for $p < 0.05$ . Given our small sample size and the low rate of complications with both analgesic methods, we expect very limited side effect data. A descriptive overall side effect rate will be calculated for each arm of the study, and the individual side effects will be listed in a table. A cost analysis will be performed, comparing the total cost of hospitalization between the cryoanalgesia and epidural groups. Difference in total cost will be assessed with two-tailed unpaired t test.

Rationale for Number of Subjects	
We used the UCSF Clinical & Translational Science Institute web-based sample size calculator (http://www.sample-size.net/sample-size-means/) to determine study size. Based on previous Nuss procedures over the past 2 years at our institution, we determined the mean length of hospitalization was 7 days, with a standard deviation of 1.3 days. From anecdotal data from our prior experience, as well as from speaking with other surgeons utilizing cryoablation, we expect patients in the cryoanalgesia group to have approximately 2 days shorter hospital stay. With type I error rate of 0.05 and type II error rate of 0.1 (yielding 90% power), our study would need 18 patients total. Allowing for some dropout, we will plan to enroll 20 patients to the study.

---	---

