### **12.4 Replacement of Subjects**

Subjects who withdraw from the study treatment will not be replaced.

Subjects who withdraw from the study will not be replaced.

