### 14.3 Analysis of Primary Endpoint

Our primary outcome will be post-operative hospital length of stay, which will be analyzed using a two-tailed unpaired t test, with results considered statistically significant for  $p < 0.05$ .

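### Eighteen patients give the planned t test 86.5% power, not 90%; reaching 90% takes all 20, so there is no dropout allowance

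*Combined protocol and SAP*

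**What the plan says.** Section 14.5 takes its planning values from the institution's own experience: "we determined the mean length of hospitalization was 7 days, with a standard deviation of 1.3 days". It expects the cryoanalgesia group to stay about 2 days less, on anecdotal grounds. It then sets the error rates, "With type I error rate of 0.05 and type II error rate of 0.1 (yielding 90% power"), and concludes: "our study would need 18 patients total. Allowing for some dropout, we will plan to enroll 20 patients to the study". No dropout rate is given; 2 of 20 implies 10%. The synopsis repeats the claim: "With type I error rate of 0.05 and type II error rate of 0.1 (yielding 90% power), our study would need 18 patients total".

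Three other parts of the protocol bear on this:

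- Section 14.3 says of the primary outcome that it will be "analyzed using a two-tailed unpaired t test", significant at p < 0.05.
- Section 12.4: "Subjects who withdraw from the study will not be replaced".
- Section 14.1 restricts the analysis to eligible randomized patients who receive the initial analgesic and undergo the Nuss procedure.

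Allocation is 1:1 (synopsis and section 4.1).

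**The concern.** In a trial this small, the choice between normal and t quantiles matters. A sample size from the normal formula is too low for a t test by about one patient per arm, which here is about a tenth of the trial. If 18 came from the normal formula, 90% power at 18 is not a property of the planned test, and the margin from 18 to 20 is already used up in reaching the target.

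Two things are at stake. The first is the accuracy of the stated type II error at the evaluable size the protocol says it needs. The second is whether the trial can lose any patient and keep its stated power, given that the protocol expects some dropout and does not replace withdrawals.

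**Working it through.** **Inputs.** From section 14.5: difference δ = 2 days, SD σ = 1.3 days, type I error 0.05, power 0.90. From section 14.3: two-sided unpaired t test. From the synopsis and section 4.1: 1:1 allocation. One assumption is added: the same SD in both arms, because none is given for cryoanalgesia.

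**Step 1: reproduce the stated 18.** The normal-approximation formula is

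n per arm = 2(z₀.₉₇₅ + z₀.₉₀)² σ² / δ²

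= 2 × (1.96 + 1.2816)² × 1.3² / 2² = 8.88, rounded up to 9 per arm, or 18 in total.

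This matches the protocol. On the same normal approximation, power at 9 per arm is 90.4%.

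**Step 2: power of the planned test at 18.** For the pooled t test,

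- degrees of freedom = n₁ + n₂ − 2 = 16
- two-sided critical value = 2.12
- noncentrality = δ / [σ √(1/n₁ + 1/n₂)] = 2 / (1.3 × √(2/9)) = 3.26

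The noncentral t distribution then gives power of 86.5%, a type II error of 13.5%. A simulation of 400,000 trials also gave 86.5%.

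**Step 3: size at which the planned test reaches 90%.** Solving the noncentral t power for 0.90 gives 9.95 per arm, so 10 per arm. As a check, the normal result plus the usual small-sample correction z²/4 is 8.88 + 0.96 = 9.84, which also rounds up to 10.

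| Patients analysed | Power, two-sided t test |
|---|---|
| 9 + 9 = 18 | 86.5% |
| 10 + 8 = 18 | 86.1% |
| 10 + 9 = 19 | 88.4% |
| 10 + 10 = 20 | 90.2% |

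**Step 4: would another reading rescue 18?** The unequal-variance (Welch) form gives simulated power of 86.1% at 18 and 90.0% at 20, so the conclusion is unchanged. A one-sided 0.05 t test would have 93.0% at 18, but section 14.3 and the synopsis both specify two-tailed.

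**Step 5: sensitivity at 20 patients.** Power of 90% holds only while the SD is no more than about 1.304. As illustrations with values that are not in the protocol, an SD of 1.4 gives 85.5%, an SD of 1.5 gives 80.5%, and a true difference of 1 day at SD 1.3 gives 37%.

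**The case against.** There are four serious points on the other side.

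- **Eighteen is not a slip of arithmetic.** It follows exactly from a standard large-sample formula. The protocol does not say which formula the web calculator used, so the normal formula is an inference from the matching result. Both points stand. The fault is better described as an approximation that does not fit the planned test. The power of that test at 18 is 86.5% whichever formula produced the number.
- **The trial as enrolled meets its target.** Twenty patients give 90.2%, and losing one or two leaves 86% to 88%. This is true and limits the weight of the point. It also means the target is met only with no loss at all.
- **Losses on this endpoint may be few.** Length of stay runs from surgery to discharge (section 5.1), so withdrawal during the year of follow-up need not cost a primary outcome. That largely stands. Patients can still leave the analysis before or around surgery: section 14.1 excludes those without the initial analgesic or the operation, and section 10.2 puts the pregnancy test on the day of surgery, with pregnancy an exclusion.
- **The planning values are softer than 3.5 points of power.** The 2-day effect is approximate and anecdotal. Eighteen patients would reach 90% if the difference were 2.12 days, or give 91.3% if the SD were 1.2. This is fair, but it works in both directions, as the illustrative SDs of 1.4 and 1.5 show.

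These points bear on weight and wording. None makes the stated power at 18, or the dropout allowance, correct.

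**Conclusion.** The concern holds. On the protocol's own planning values, with a common SD and the two-sided t test of section 14.3, 18 patients give 86.5% power, 3.5 points below the stated 90%. Ninety per cent is first reached at 20 analysed patients (90.2%). Nothing is held in reserve for dropout at that power. The practical effect is modest: no patient needs to be added, and two losses would leave power at about 86%. The figures are wrong as written and should be corrected.

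**What to change.** In section 14.5 and the matching synopsis paragraph, replace the sample size conclusion with wording such as: Using the t distribution, 20 evaluable patients (10 per arm) give 90% power to detect a 2-day difference with an SD of 1.3 days; if 18 are evaluable, power is about 86%. Delete the statement that 20 allows for dropout. Carry the same wording into the separate SAP that section 14 promises.

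A useful but separable addition is a sentence on precision. With 20 patients and SD 1.3, the expected 95% confidence interval half-width is about 2.10 × 1.3 × √(2/10) = 1.22 days, so a non-significant result should be read from the interval and not as showing no benefit, an outcome that section 2.1 contemplates. The main correction does not depend on it.

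The cost is two sentences in two places and a slightly less favourable stated figure. Enrolment, design and analysis stay as they are.

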## 15 DATA COLLECTION, RETENTION AND MONITORING

### 15.1 Data Collection Instruments

The Investigator will prepare and maintain adequate and accurate source documents designed to record all observations and other pertinent data for each subject treated with the study drug.

Study personnel at each site will enter data from source documents corresponding to a subject's visit into the protocol-specific electronic Case Report Form (eCRF) OR paper CRF when the information corresponding to that visit is available. Subjects will not be identified by name in the study database or on any study documents to be collected by the Sponsor (or designee), but will be identified by a subject number.

*For eCRFs:* If a correction is required for an eCRF, the time and date stamps track the person entering or updating eCRF data and creates an electronic audit trail. *For paper CRFs:* If a correction is made on a CRF, the study staff member will line through the incorrect data, write in the correct data and initial and date the change.

The Investigator is responsible for all information collected on subjects enrolled in this study. All data collected during the course of this study must be reviewed and verified for completeness and accuracy by the Investigator.

### 15.2 Data Management Procedures

The data will be entered into a validated database. The Data Management group will be responsible for data processing, in accordance with procedural documentation. Database lock will occur once quality assurance procedures have been completed.

All procedures for the handling and analysis of data will be conducted using good computing practices meeting FDA guidelines for the handling and analysis of data for clinical trials.

### 15.3 Data Quality Control and Reporting

After data have been entered into the study database, a system of computerized data validation checks will be implemented and applied to the database on a regular basis. The study database will be updated in accordance with the resolved queries. All changes to the study database will be documented.

### 15.4 Archival of Data

The database is safeguarded against unauthorized access by established security procedures; appropriate backup copies of the database and related software files will be maintained. Databases are backed up by the database administrator in conjunction with any updates or changes to the database.

At critical junctures of the protocol (e.g., production of interim reports and final reports), data for analysis is locked and cleaned per established procedures.

### **15.5 Availability and Retention of Investigational Records**

The Investigator must make study data accessible to the monitor, other authorized representatives of the Sponsor (or designee), IRB/IEC, and Regulatory Agency (e.g., FDA) inspectors upon request. A file for each subject must be maintained that includes the signed Informed Consent, HIPAA Authorization and Assent Form and copies of all source documentation related to that subject. The Investigator must ensure the reliability and availability of source documents from which the information on the CRF was derived.

All study documents (patient files, signed informed consent forms, copies of CRFs, Study File Notebook, etc.) must be kept secured for a period of two years following marketing of the investigational product or for two years after centers have been notified that the IND has been discontinued. There may be other circumstances for which the Sponsor is required to maintain study records and, therefore, the Sponsor should be contacted prior to removing study records for any reason.

### **15.6 Monitoring**

Monitoring visits will be conducted by representatives of the Sponsor according to the U.S. CFR Title 21 Parts 50, 56, and 312 and ICH Guidelines for GCP (E6). By signing this protocol, the Investigator grants permission to the Sponsor (or designee), and appropriate regulatory authorities to conduct on-site monitoring and/or auditing of all appropriate study documentation.

### **15.7 Subject Confidentiality**

In order to maintain subject confidentiality, only subject number will identify all study subjects on CRFs and other documentation submitted to the Sponsor. Additional subject confidentiality issues (if applicable) are covered in the Clinical Study Agreement.

## **16 ADMINISTRATIVE, ETHICAL, REGULATORY CONSIDERATIONS**

The study will be conducted according to the Declaration of Helsinki, Protection of Human Volunteers (21 CFR 50), Institutional Review Boards (21 CFR 56), and Obligations of Clinical Investigators (21 CFR 312).

To maintain confidentiality, all laboratory specimens, evaluation forms, reports and other records will be identified by a coded number and initials only. All study records will be kept in a locked file cabinet and code sheets linking a patient's name to a patient identification number will be stored separately in another locked file cabinet. Clinical information will not be released without written permission of the subject, except as necessary for monitoring by the FDA. The Investigator must also comply with all applicable privacy regulations (e.g., Health Insurance Portability and Accountability Act of 1996, EU Data Protection Directive 95/46/EC).

### **16.1 Protocol Amendments**

Any amendment to the protocol will be written by the investigator. Protocol amendments cannot be implemented without prior written IRB/IEC approval except as necessary to eliminate immediate safety hazards to patients. A protocol amendment intended to eliminate an apparent immediate hazard to patients may be implemented immediately, provided the IRBs are notified within five working days.

## 16.2 Institutional Review Boards and Independent Ethics Committees

The protocol and consent form will be reviewed and approved by the IRB/IEC of each participating center prior to study initiation. Serious adverse experiences regardless of causality will be reported to the IRB/IEC in accordance with the standard operating procedures and policies of the IRB/IEC, and the Investigator will keep the IRB/IEC informed as to the progress of the study. The Investigator will obtain assurance of IRB/IEC compliance with regulations.

Any documents that the IRB/IEC may need to fulfill its responsibilities (such as protocol, protocol amendments, Investigator's Brochure, consent forms, information concerning patient recruitment, payment or compensation procedures, or other pertinent information) will be submitted to the IRB/IEC. The IRB/IECs written unconditional approval of the study protocol and the informed consent form will be in the possession of the Investigator before the study is initiated. This approval must refer to the study by exact protocol title and number and should identify the documents reviewed and the date of review.

Protocol and/or informed consent modifications or changes may not be initiated without prior written IRB/IEC approval except when necessary to eliminate immediate hazards to the patients or when the change(s) involves only logistical or administrative aspects of the study. Such modifications will be submitted to the IRB/IEC and written verification that the modification was submitted and subsequently approved should be obtained.

The IRB/IEC must be informed of revisions to other documents originally submitted for review; serious and/or unexpected adverse experiences occurring during the study in accordance with the standard operating procedures and policies of the IRB; new information that may affect adversely the safety of the patients of the conduct of the study; an annual update and/or request for re-approval; and when the study has been completed.

## 16.3 Informed Consent Form

Informed consent will be obtained in accordance with the Declaration of Helsinki, ICH GCP, US Code of Federal Regulations for Protection of Human Subjects (21 CFR 50.25[a,b], CFR 50.27, and CFR Part 56, Subpart A), the Health Insurance Portability and Accountability Act (HIPAA, if applicable), and local regulations.

The Investigator will prepare the informed consent form, assent and HIPAA authorization and provide the documents to the Sponsor or designee for approval prior to submission to the IRB/IEC. The consent form generated by the Investigator must be acceptable to the Sponsor and be approved by the IRB/IEC. The written consent document will embody the elements of informed consent as described in the International Conference on Harmonisation and will also comply with local regulations. The Investigator will send an IRB/IEC-approved copy of the Informed Consent Form to the Sponsor (or designee) for the study file.

A properly executed, written, informed consent will be obtained from each subject prior to entering the subject into the trial. Information should be given in both oral and written form and subjects (or their legal representatives) must be given ample opportunity to inquire about details of the study. If appropriate and required by the local IRB/IEC, assent from the subject will also be obtained. If a subject is unable to sign the informed consent form (ICF) and the HIPAA authorization, a legal representative may sign for the subject. A copy of the signed consent form (and assent) will be given to the subject or legal representative of the subject and the original will be maintained with the subject's records.

#### **16.4 Publications**

The preparation and submittal for publication of manuscripts containing the study results shall be in accordance with a process determined by mutual written agreement among the study Sponsor and participating institutions. The publication or presentation of any study results shall comply with all applicable privacy laws, including, but not limited to, the Health Insurance Portability and Accountability Act of 1996.

#### **16.5 Investigator Responsibilities**

By signing the Agreement of Investigator form, the Investigator agrees to:

1. Conduct the study in accordance with the protocol and only make changes after notifying the Sponsor (or designee), except when to protect the safety, rights or welfare of subjects.
2. Personally conduct or supervise the study (or investigation).
3. Ensure that the requirements relating to obtaining informed consent and IRB review and approval meet federal guidelines, as stated in § 21 CFR, parts 50 and 56.
4. Report to the Sponsor or designee any AEs that occur in the course of the study, in accordance with §21 CFR 312.64.
5. Ensure that all associates, colleagues and employees assisting in the conduct of the study are informed about their obligations in meeting the above commitments.
6. Maintain adequate and accurate records in accordance with §21 CFR 312.62 and to make those records available for inspection with the Sponsor (or designee).
7. Ensure that an IRB that complies with the requirements of §21 CFR part 56 will be responsible for initial and continuing review and approval of the clinical study.
8. Promptly report to the IRB and the Sponsor (or designee) all changes in the research activity and all unanticipated problems involving risks to subjects or others (to include amendments and IND safety reports).
9. Seek IRB approval before any changes are made in the research study, except when necessary to eliminate hazards to the patients/subjects.
10. Comply with all other requirements regarding the obligations of clinical investigators and all other pertinent requirements listed in § 21 CFR part 312.

## APPENDIX 1. SCHEDULE OF STUDY VISITS

	VISIT 1 pre-op	VISIT 2 procedure/hospit alization	VISIT 3 2 weeks post-op	VISIT 4 1 MONTH POST-OP	VISIT 5 3 MONTHS POST-OP	VISIT 6 1 YEAR POST-OP
Informed Consent	X					
Medical History	X					
Complete Physical Exam	X					
Abbreviated Physical Exam		X	X	X	X	X
Height	X	X				
Weight	X	X				
Vital Signs	X	X	X	X	X	X
Oximetry	X	X	X	X	X	X
Randomization	X					
Urine Pregnancy Test (females)		X				
Administration of Initial Analgesia (cryo vs. epidural)		X				
Survey Administration		X	X	X	X	X
Documentation of Pain Medication Usage		X	X	X	X	X
Counting of Returned Post-op Pain Medication			X	X	X	X
Initiate Subject Diary		X				
Subject Diary Review			X	X	X	X
Concomitant Medication Review	X	X	X	X	X	X
Adverse Experiences		X	X	X	X	X
